Study Design: This is a multicenter, open-label study designed to assess the long-term safety and efficacy of AMG 334. Subjects who complete the 12-week double-blind treatment phase of the AMG 334 20120295 parent study and meet all AMG 334 20130255 eligibility criteria will be enrolled into the study. Enrollment should occur within 14 days of the week 12 visit of the AMG 334 20120295 parent study. Subjects who enroll in the AMG 334 20130255 study will end the AMG 334 20120295 study and will not participate in the parent study safety follow-up visit. Subjects may also elect to participate in a Novel Patient-reported Outcome Substudy in addition to a CHU substudy.

All subjects who have not yet enrolled in the study will receive open-label AMG 334 140 mg every month (QM) subcutaneous (SC) for 13 months. Subjects who are already enrolled in the 20130255 study will increase the open-label dose from 70 mg QM to 140 mg QM at the first available opportunity at either week 4, 8, 12, 16, 20, 24, or 28 visits. Subjects who have already

completed the week 28 visit will continue to receive 70 mg QM. Subjects will not have the option to decrease open-label AMG 334 from 140 mg QM to 70 mg QM. The 13-month open-label AMG 334 treatment phase will be followed by a 12-week safety follow-up visit (16 weeks after last dose of investigational product).

Sample Size: All subjects who completed the 12-week double-blind treatment phase of the AMG 334 20120295 parent study, meet the inclusion and exclusion criteria for the AMG 334 20130255 OLE study will be eligible to be enrolled. Up to 651 subjects may participate in the study.

Summary of Subject Eligibility Criteria: Adults with history of chronic migraine and who completed the 12-week double-blind treatment phase of the parent study. For a full list of eligibility criteria, please refer to [Section 4.1](#).

Amgen Investigational Product Dosage and Administration: Investigational product (IP) (ie, AMG 334 70 mg or 140 mg) will be dosed QM by SC injection. **For subjects participating in the CHU substudy, IP is AMG 334 140 mg in either a PFS or prefilled AI/Pen.**

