3. EXPERIMENTAL PLAN

3.1 Study Design

This is a multicenter, open-label study designed to assess the long-term safety and efficacy of AMG 334. Subjects who complete the 12-week double-blind treatment phase of the AMG 334 20120295 parent study and meet all AMG 334 20130255 eligibility criteria will be enrolled into the study. Enrollment should occur within 14 days after the parent study's week 12 visit. Subjects who enroll in the AMG 334 20130255 study will end the AMG 334 20120295 study and will not participate in the parent study safety follow-up visit.

All subjects who have not yet enrolled in the study will receive open-label AMG 334 140 mg every month (QM) SC for 13 months. Subjects who are already enrolled in the 20130255 study will increase the open-label dose from 70 mg QM to 140 mg QM at the first available opportunity at either week 4, 8, 12, 16, 20, 24, or 28 visits. Subjects who have already completed the week 28 visit will continue to receive 70 mg QM.

All subjects will receive open-label AMG 334 QM SC for 13 months followed by a 12-week safety follow up visit (16 weeks after the last dose of investigational product [IP]).

Investigational product (ie, AMG 334 70 mg or 140 mg) will be dosed QM, SC.

The overall study design is described by a [study schema](#) at the end of the protocol synopsis section.

The study endpoints are defined in [Section 10.1.1](#).

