- ^g Screening must occur 4 weeks prior to the planned start of the CHU substudy (week 8 or week 36 of the 20130255 study). IVR System will be adjusted to accommodate CHU screening and randomization information as required.
- ^h Day 1 of the CHU is equivalent to either week 12 or week 40 of the 20130255 study.
- ⁱ Day 28 of the CHU is equivalent to either week 16 or week 44 of the 20130255 study.
- ^j Day 56 of the CHU is equivalent to either week 20 or week 48 of the 20130255 study.
- ^k Day 85 of the CHU is equivalent to either week 24 or week 52 of the 20130255 study; subject will receive AMG 334 140mg SC administered by site staff using vial formulation and will continue scheduled procedures and assessments as per 20130255 study.
- ^l ET: If a subject early terminates the CHU substudy, he/she may receive administration of AMG 334 140 mg SC at site as per 20130255 protocol and will continue 20130255 scheduled procedures and assessments as per 20130255 protocol.
- ^m Study coordinator will review PFS or AI/pen training materials (Reference Guide and Instructions for Use) with subject.

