7.2.1.15 Novel PRO Instrument Substudy (Optional)

Subjects may elect to participate in a separate novel PRO substudy to evaluate the impact of migraine. Subjects may elect to participate in both the Novel PRO Instrument substudy and the CHU substudy. The MPFID, a self-administered 13-item instrument that measures physical functioning, will be used to measure physical impairment and the impact of migraine on subjects' everyday activities. Participation in the substudy is optional. Subjects who elect to participate in this PRO substudy will be required to provide separate informed consent and must be willing to complete the MPFID daily during the study timepoints noted below. Approximately 200 subjects will participate in this substudy.

The Migraine Physical Function Impact Diary (MPFID)

CCI

CCI

Subjects participating in the novel PRO substudy will complete the MPFID every day using the eDiary between the Day 1 and month 3 visit, between the month 5 and 6 visit, between the month 9 and 10 visit, and between the month 12 and 13 visit. Subjects may begin to participate in the substudy at any time on or before the month 12 visit.

7.2.1.16 Clinical Home Use Substudy (Optional; Limited to Subjects in US, Germany and Sweden)

Up to 80 subjects may elect to participate in a separate CHU substudy to assess subjects' ability to self-administer 140 mg of AMG 334 for in-home use using either two PFS or two prefilled AI/pens. It is hypothesized that users will be able to self-administer a full dose of AMG 334 comparably using either the PFS or AI/pen. No formal hypotheses will be tested. Safety and tolerability of AMG 334 self-administered using two 1-mL PFS or two 1-mL AI/pens will also be assessed. Participation in the substudy is optional and no additional samples are collected for the substudy. Subjects who elect to participate in this CHU substudy will be required to provide separate informed consent and must meet the following inclusion and none of the exclusion criteria:

Inclusion Criteria: Subjects entering the substudy at week 12 of the 20130255 study must have received open-label 140 mg AMG 334 since day 1 of the 20130255 study. Subjects entering the substudy at week 40 must have received open-label 140 mg AMG 334 since week 28 of the 20130255 study or earlier.

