event, **serious adverse event**, and concomitant medication assessment, vital signs measurement, ECGs, urinalysis, and blood draw for serum chemistry and hematology analytes and anti-AMG 334 antibody assay will be performed as described in the 20130255 study. Subjects will be randomized to self-administer either 2x70mg AMG 334 via PFS or 2x70mg AMG 334 via **prefilled** AI/pen. On the CHU day 1 visit (week 12 or week 40 of AMG 334 20130255 study) the site should review the IFU and RG for AI/pen or PFS with the subject prior to administration of IP (depending upon device subject has been randomized to use). On day 1 of the substudy, subjects will self-administer IP, AMG 334 140 mg SC with either two x 70 mg **prefilled** AI/pen or two x 70 mg PFS, under clinical site supervision. Subjects will be provided a box containing either 2x70 mg PFS or 2x70 mg **prefilled** AI/pen at the CHU day 28 (week 16 or week 44 of AMG 334 20130255 study) and day 56 (week 20 or week 48 of AMG 334 20130255 study) visits and will self-administer IP individually without supervision at home on days 29 and 57 of the CHU substudy. On CHU day 29 and day 57, site staff will call the subject at a previously scheduled time and will ask the subject which injection site was used, if the subject administered a full, partial, or no dose of AMG 334 (after explaining that a full dose means that the entire volume of both PFS or AI/pens were injected) and will document the subject's response in the CRF. If the subject was not able to administer a full dose of AMG 334, the site staff will inquire further to determine if the subject experienced a device failure or use error that prevented the full-dose administration. Safety will be monitored as adverse events, serious adverse events, and ADEs. Day 85 is the end of the CHU substudy and sites will inquire about ADEs. Day 85 of the CHU substudy is equivalent to either week 24 or week 52 of the 20130255 study; site will administer AMG 334 140 mg SC and will continue 20130255 scheduled procedures and assessments as per the 20130255 protocol. If a subject early terminates the CHU substudy, he/she may receive administration of AMG 334 140 mg SC at site as per the 20130255 protocol and will continue 20130255 scheduled procedures and assessments as per the 20130255 protocol. Subjects who elect to early terminate the CHU substudy will not be replaced.

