 - Telephone call time scheduled for day 29 (Note, telephone visit must occur after subject has self-administered IP)
 - Product Complaint Recording (if applicable)
 - Day 29:
 - Subject self-administers AMG 334 using either PFS or **prefilled** Al/pen in non-clinic setting
 - Telephone visit with study coordinator to inquire of subject if he/she administered a full, partial, or no dose of AMG 334
 - If the subject was not able to administer a full dose of AMG 334, the site staff will inquire further to determine if the subject experienced a device failure or use error that prevented the full-dose administration

- Review adverse events/ADEs/serious adverse events
- Product Complaint Recording (if applicable)
- Day 56 (20130255 week 20 or 48):
 - Study coordinator dispenses PFS or **prefilled** AI/pen to subject for self-administration on day 57
 - Telephone call time scheduled for day 57 (Note, telephone visit must occur after subject has self-administered IP)
 - Product Complaint Recording (if applicable)
- Day 57:
 - Subject self-administers AMG 334 using either PFS or **prefilled** AI/pen in non-clinic setting
 - Telephone visit with study coordinator to inquire of subject if he/she administered a full, partial, or no dose of AMG 334
 - If the subject was not able to administer a full dose of AMG 334, the site staff will inquire further to determine if the subject experienced a device failure or use error that prevented the full-dose administration
 - Review adverse events/ADEs/serious adverse events
 - Product Complaint Recording (if applicable)
- Day 85 (20130255 week 24 or 52): End of CHU substudy
 - Study coordinator inquires about any ADEs, product complaint recording (if applicable)
 - Subject continues all 20130255 study assessments and IP is administered at site as per 20130255 protocol using vial formulation

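### Table 1 footnote k and Section 7.2.1.16 direct a 140 mg site dose at CHU Day 85 that, for week-40 entrants, falls at week 52, where the dosing schedule has none

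*Protocol*

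**What the plan says.** The main schedule in protocol Table 1 marks product administration on Day 1 and at every four-weekly visit from week 4 to week 48. The row is blank at week 52 and at the safety follow-up visit. The follow-up visit is labelled week 64 and tied to the last dose. The synopsis describes it as a "12-week safety follow-up visit (16 weeks after last dose of investigational product"), and Section 3.1 says the same.

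The CHU substudy (Section 7.2.1.16) takes up to 80 subjects and can be entered at week 12 or week 40. The second route is explicit: "Subjects entering the substudy at week 40 must have received open-label 140 mg AMG 334 since week 28" or earlier. Subjects inject on site on CHU Day 1 and then "self-administer IP individually without supervision at home on days 29 and 57 of the CHU substudy".

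Four places deal with a site dose at the end of the substudy:

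- Table 1, footnote k: Day 85 is "week 24 or week 52 of the 20130255 study; subject will receive AMG 334 140mg SC administered by site staff using vial formulation".
- Section 7.2.1.16: Day 85 is "equivalent to either week 24 or week 52 of the 20130255 study; site will administer AMG 334 140 mg SC".
- Section 7.2.4, Day 85 list: "IP is administered at site as per 20130255 protocol using vial formulation".
- Table 1, footnote l (early termination of the substudy): "he/she may receive administration of AMG 334 140 mg SC at site as per 20130255 protocol".

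The first two name week 52 and direct a dose. The last two tie the dose to the main protocol.

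**The concern.** Footnote k and Section 7.2.1.16 each give one instruction for two entry groups whose Day 85 falls at different points of the main schedule. It is right for one group and contradicts the main schedule for the other. A site with a week-40 entrant cannot comply with everything: dosing at week 52 departs from the main part of Table 1, and withholding departs from footnote k and Section 7.2.1.16.

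What is at stake is mainly subject protection: a dose of an investigational product that the schedule does not contain. The obligations that run from the last dose (contraception, adverse event collection, pregnancy reporting, the follow-up visit) would shift with it.

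**Working it through.** **Inputs.** Dosing visits: Table 1, product administration row. Follow-up timing: synopsis, Section 3.1 and the Table 1 column label. CHU anchors: Table 1 footnotes h to k. Target days: SAP 6.4, week 4n on day 28n + 1, so week w is day 7w + 1. Adverse event window: SAP 6.4, the earlier of end of study and last dose + 112 days. Exposure: SAP 6.6, last dose date + 27 (or end of study if earlier) − first dose date + 1.

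**1. Reproduce the plan's follow-up week.** Scheduled doses: 1 + 12 = 13, the last at week 48. Week 48 + 16 = week 64, as Table 1 states. Week 52 + 12 = week 64 as well. The 12-week and 16-week descriptions therefore agree only if the last dose is at week 48. With a last dose at week 52 they would point to weeks 64 and 68.

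**2. Place the CHU days.** CHU Day d for entry week e is study day 7e + d.

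| CHU day | Week-12 entrant | Week-40 entrant |
|---|---|---|
| 1 | day 85, week 12 | day 281, week 40, dose 11 |
| 29 | day 113, week 16 | day 309, week 44, dose 12 |
| 57 | day 141, week 20 | day 337, week 48, dose 13 |
| 85 | day 169, week 24: dose scheduled | day 365, week 52: no dose scheduled |

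Week-12 entrants end with 13 doses. Week-40 entrants end with 13 under Table 1 and 14 under the literal Day 85 instruction, assuming no earlier missed dose. The extra dose comes 365 − 337 = 28 days after the previous one.

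**3. Follow-up after a week-52 dose.**

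- Visit held 16 weeks after the actual last dose: day 365 + 112 = 477 (week 68). The adverse event window ends at min(477, 477) = 477, which is 28 days later than day 449.
- Visit left at week 64: day 449 − 365 = 84 days after the last dose instead of 112 (76 to 92 with ±4 days on both visits). The window ends at min(449, 477) = 449, unchanged. Serum pregnancy, PK and antibody samples would then be taken 12 weeks after the last dose.

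**4. Effect on analyses.**

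- Adverse event follow-up: 28/365.25 = 0.077 subject-years per affected subject if the visit moves. Upper bound, assuming all 80 CHU subjects entered at week 40 and all 651 subjects completed: 80 × 28/365.25 = 6.13 of 651 × 449/365.25 = 800.3 subject-years, or 0.77%. With 40 such subjects (assumed): 3.07, or 0.38%. Both ignore the stop at first event.
- Exposure groups: duration 337 + 27 = 364 days becomes 365 + 27 = 392. The 140 mg share after escalation at week w goes from 1 − 7w/364 to 1 − 7w/392. At week 8 it is 84.6% then 85.7%; at week 12, 76.9% then 78.6%; at week 28, 46.2% then 50.0%. No escalation week from 4 to 28 crosses the 80% limit.
- Efficacy: the last interval in SAP 6.4 ends on study day 364, before any day-365 dose.

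**5. Study length.** Week 68 is 476/30.4375 = 15.6 calendar months, within the 16 months planned in Section 3.5.1. It exceeds 16 only if months are counted as four weeks (68/4 = 17).

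**The case against.** The strongest reply is that the intended rule can be recovered. Section 7.2.4 and footnote l tie the dose to the main protocol. The CHU part of Table 1 has no site-dosing row at Day 85. SAP 6.5 treats completion of week 52 as including a completed end-of-product form. The mention of vials in footnote k suggests that its purpose is the return from device to vial. The closing reference to the main study in both instructions might be stretched to cover the dose as well as the assessments. Kits are assigned through the IVR/IWR system, which may release nothing at week 52.

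Most of this stands as evidence of intent. A reader might infer from footnote k that a 14th dose was planned; the documents do not support that. Nor do they show that anyone would receive one: they do not say how the IVR/IWR system is set at week 52, and footnote g mentions adjustment only for CHU screening and randomization. But evidence of intent does not cancel two explicit instructions that name week 52. Section 7.2.4 never says that there is no dose then, and footnote l is permissive where footnote k is directive, a difference a coordinator could take as deliberate.

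Three further inferences go too far:

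- **Shortened follow-up.** The 84-day interval needs a second error: a site would have to give the dose and then disregard the rule that fixes the visit 16 weeks after the last dose. Contraception, adverse event collection and pregnancy reporting also run from the last dose and extend on their own.
- **A breach of Section 3.5.1.** That section states a planned length, and week 68 is under 16 calendar months.
- **Overdosing.** The dose would be 140 mg four weeks after the last one, the regimen these subjects already follow.

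**Conclusion.** The point holds as an internal inconsistency in a dosing instruction. Followed as written, footnote k and Section 7.2.1.16 give week-40 CHU entrants one unscheduled 140 mg dose at week 52, against Table 1, Section 7.2.4 and the follow-up timing. It is a missing exception, not a design choice.

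Reach is limited to week-40 entrants. The documents do not state their share of the 80 or fewer CHU subjects. No efficacy estimate or exposure-group assignment changes, and the effect on pooled adverse event rates is negligible even at the upper bound. The calculations use target days and assume no missed doses. The gain from correcting the text is that sites do not give an unscheduled investigational dose and that the week-64 visit stays 16 weeks after the last dose.

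**What to change.** In Table 1 footnote k and in Section 7.2.1.16, limit the Day 85 site-administered 140 mg dose to subjects who entered the substudy at week 12, for whom Day 85 is week 24. In both places, state that subjects who entered at week 40 receive no product at week 52. Notify sites. Both entry groups then have 13 scheduled doses ending at week 48, and day 337 + 112 = day 449 is week 64.

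The cost is one clause in each place and a site memo. Section 3.5.1 and the SAP need no change: a dose given inadvertently at week 52 is already covered by the existing rule that follow-up takes place 16 weeks after the last dose, and SAP 6.4 takes the follow-up visit by its nominal label, so a later visit is still analysed.

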7.2 General Study Procedures

7.2.1 Study Specific Assessments

7.2.1.1 Informed Consent

All subjects or legally authorized representatives must personally sign and date the Amgen/IRB/IEC approved ICF before any study-specific procedures are performed.

7.2.1.2 Calls to Interactive Voice Response (IVR) / Interactive Web Response (IWR) System

Sites are to call the Interactive Voice Response (IVR) / Interactive Web Response (IWR) System for the following: to enroll an eligible subject, to obtain the investigational product assignment, to register the end of investigational product, and to register study early termination (ET) or completion. Subject data will be collected in the IVR/IWR system.

7.2.1.3 Physical Examination

A complete physical examination (PE) per standard of care (including neurological exam) will be performed on all subjects.

7.2.1.4 Weight Measurements

Weight is to be measured without shoes and is to be recorded on the Physical Measurements CRF.

7.2.1.5 Vital Signs

The following measurements are to be performed: Systolic/diastolic blood pressure, heart rate, and body temperature.

Blood pressure will be measured in the following manner:

- Subjects should be lying in a supine position quietly and comfortably for at least 5 minutes. The upper arm should be bare without constrictive clothing and supported at heart level (such as with a pillow approximately 13 centimeters tall).
- Caffeine, exercise, and smoking should be avoided for at least 30 minutes prior to measurement.
- An appropriately-sized cuff (cuff bladder encircling at least 80 percent of the arm) should be used to ensure accuracy. At least two measurements (separated by at least 5 minutes) should be made and the average recorded. If there is a high value, it is acceptable to wait approximately 30 minutes before the next two blood pressure measurements are taken for the purpose of averaging and recording in the CRF.
- Neither the subject nor the observer (measurer) should talk during measurement.

The position selected for a subject should be the same that is used throughout the study and documented on the Vital Signs CRF.

If the screening systolic BP is > 160 mm Hg or diastolic BP is > 100 mm Hg when initially assessed, BP may be repeated 30 minutes after the initial measurement. BP measurements may only be repeated once after the initial measurement.

The temperature location selected for a subject should be the same that is used throughout the study and documented on the Vital Signs CRF.

All measurements are to be recorded on the Vital Signs CRF.

7.2.1.6 Urine Drug Screening

During the study, urine drug tests may be performed at the investigator's discretion based on clinical suspicion. Urine samples will be analyzed by the central laboratory. For a subject with a positive urine drug screen during the study (except for certain prescribed medications), the investigator should consider discontinuing the subject from investigational product.

7.2.1.7 Pregnancy Testing for Women of Childbearing Potential

Female subjects of childbearing potential will have urine pregnancy tests throughout the treatment phase and a serum pregnancy test at the safety follow-up visit. All urine pregnancy testing will be performed by the local laboratory.

7.2.1.8 Electrocardiogram (ECG)

The subject must be in a supine position in a rested and calm state for at least 5 minutes before the ECG assessment is conducted. If the subject is unable to be in the supine position, the subject should be in most recumbent position as possible. The ECG must include the following measurements: Heart Rate, QRS, QT, QTc, and PR intervals.

Sites will use ECG equipment supplied by Amgen. It is the responsibility of the investigator to determine if the ECG tracings are consistent with a subject's safe participation in the study. The investigator will review and sign the original ECG tracing and retain the signed tracing with the subject's source documents. The central reader will review all ECGs. At the request of Amgen, a copy of the original ECG will be made available to Amgen.

Any ECG abnormality noted by the central reader must be evaluated by the investigator and discussed with the Amgen Medical Monitor as deemed necessary to determine if the ECG finding is representative of an unstable or clinically significant medical condition.

Please refer to the central ECG reader manual for details.

